2.3 Benefit/Risk Assessment

2.3.1 Risk Assessment

Table 6 Risk Assessment

Identified and potential risk of clinical significance	Summary of data/rationale for risk	Mitigation strategy
Study interventions		
AZD2811		

Identified risks associated with AZD2811 include:
 
 • neutropenia, • febrile neutropenia, • rash, • sepsis. 
The following are considered potential risks for AZD2811:
 
 • lymphocytopenia and leukocytopenia, • anemia, • thrombocytopenia, • stomatitis/oral mucositis, • diarrhoea, • nausea and vomiting, • alopecia/hair loss. 	
Potential risks for AZD2811 have been determined from nonclinical studies with AZD2811, previous clinical experience with AZD1152 (barasertib), and clinical experience with other drugs targeting inhibition of Aurora kinases.
	
Toxicity management of AZD2811 is presented in Section 8.5.1. A dermatology consultation is recommended for participants who present with rash. G-CSF is mandatory for every cycle in which participants receive AZD2811.

Durvalumab		

Identified risks associated with durvalumab include:
 
 • pneumonitis, • interstitial lung disease, • hepatitis, • diarrhea/colitis, • hypothyroidism, • hyperthyroidism, • blood TSH increased, • blood TSH decreased, • adrenal insufficiency, • type 1 diabetes mellitus, • hypophysitis/hypopituitarism and diabetes insipidus, • nephritis, • rash/dermatitis, • myocarditis, 	
This section includes identified risks and potential risks for durvalumab of an inflammatory and/or immune-mediated nature, related to the mechanism of action of durvalumab and related to mAb therapeutics in general.
	
The risks presented can be mitigated through close monitoring, early detection, and prompt treatment with corticosteroids, immunosuppressants, and/or endocrine therapy. Investigators should adhere to the Toxicity Management Guidelines (Section 8.5.2) by performing a thorough evaluation to rule out alternative etiologies.

Table 6 Risk Assessment

Identified and potential risk of clinical significance	Summary of data/rationale for risk	Mitigation strategy

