8.3.5 Adverse Events Based on Examinations and Tests

The results from the CSP-mandated laboratory tests and vital signs will be summarized in the Clinical Study Report (CSR). Deterioration as compared to baseline in CSP-mandated laboratory values, vital signs, ECGs, and clinical/neurological assessment(s) should therefore only be reported as AEs if they fulfil any of the SAE criteria, are the reason for discontinuation of treatment with the IP, or are considered to be clinically relevant as judged by the investigator (which may include, but not be limited to, consideration as to whether treatment or non-planned visits were required or other action was taken with the study intervention, e.g., dose adjustment or drug interruption).

If deterioration in a laboratory value/vital sign is associated with clinical signs and symptoms, the sign or symptom will be reported as an AE and the associated laboratory result/vital sign will be considered as additional information. Wherever possible, the reporting investigator uses the clinical, rather than the laboratory term (e.g., anemia versus low hemoglobin value). In the absence of clinical signs or symptoms, clinically relevant deteriorations in non-mandated parameters should be reported as AE(s).

Deterioration of a laboratory value, which is unequivocally due to disease progression, should not be reported as an AE/SAE.

Any new or aggravated clinically relevant abnormal medical finding at a physical examination, as compared with the baseline assessment, will be reported as an AE unless unequivocally related to the disease under study (DUS).

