Laboratory data for hematology and clinical chemistry will be summarized. The frequency of changes with respect to normal ranges between baseline and each post-treatment time point will be tabulated. Shifts from baseline to maximum value during treatment will be evaluated for urinalysis.

Vital Signs and Physical Examination

Vital sign parameters will be presented for each treatment group. Summary statistics for continuous variables cover number of participants, mean, standard deviation, minimum, quartile 1, median, quartile 3, and maximum. Frequency tables cover number and percentage of participants in the respective category.

The baseline value will be the latest result obtained prior to the start of study intervention in the induction phase.

For each scheduled post-baseline visit, descriptive statistics for all vital sign parameters will be presented for observed values and absolute change from baseline.

Changes in vital signs will be examined at each visit. Frequencies of clinically noteworthy values (defined in the SAP) occurring during the clinical study will be presented.

Details of vital sign analyses will be provided in the SAP.

All individual physical examination and targeted physical examination data will be listed only.

ECG

For the change from baseline summaries for ECG, the baseline value will be the latest result obtained prior to the start of study intervention in the induction phase.

The QTcF will be derived during creation of the reporting database using the reported ECG values (respiratory rate [RR] and QT):

$$\text{QTcF} = \text{QT}/\text{RR}^{(1/3)}, \text{ where RR is in seconds}$$

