3.2.3.5 Laboratory Data

The laboratory variables to be measured are presented in Section 8.2.4 of the [CSP](#): Table 17 (clinical chemistry), Table 18 (hematology), Table 19 (urinalysis), and Table 20 (other safety tests, including coagulation).

White blood cell (WBC) differential counts will be presented as a percentage (relative numbers of each type of WBC in relationship to the total WBC) and as an absolute value (percentage x total WBC).

If the absolute count for a particular type of blood cell (basophils, eosinophils, lymphocytes, neutrophils, monocytes and reticulocytes) is not reported, it will be derived as the total white blood cell count multiplied by the differential percentage for that cell type.

Laboratory variables will be followed-up until end of treatment visit. Data collected during safety follow-up will be presented along with data collected during the period from which the subject discontinued.

Change from baseline in hematology and clinical chemistry will be calculated for a subset of parameters at each post-dose visit, see section 3.1.2. The subset will include the following parameters:

- Hematology
 - Haemoglobin
 - WBC
 - ANC
 - Platelets
- Clinical chemistry
 - Albumin
 - Creatinine
 - Creatinine clearance
 - Total bilirubin

- AST
- ALT
- Amylase
- Lipase
- Coagulation
 - International Ratio (INR)
 - Fibrinogen

CTC grade will be calculated at each visit. Maximum post-baseline CTC by study phase and overall will also be calculated. Clinically important changes are defined as CTCAE grade ≥ 2 or changes to CTCAE grade 3 or 4 and will be derived by study phase and overall. End of treatment results will be those which are assessed on the latest nominal visit prior or on the date subjects discontinue or complete study intervention. Absolute values will be compared to the local laboratory reference range and classified as low (below range), normal (within range or on limits of range) and high (above range). All values classified as high or low will be flagged on the listings.

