4.2.3.3 Laboratory

Clinical chemistry, coagulation and hematology results and change from baseline will be summarized using descriptive statistics (number of observations, mean, standard deviation, minimum, lower quartile, median, upper quartile and maximum) at each scheduled assessment time for continuous laboratory assessments). For a subset of laboratory variables (see Section 3.2.3.5) included in the current version of CTCAE, the CTCAE grade change from baseline to maximum on treatment will be summarized by phase. Urinalysis results will be listed only.

Number and percentages of clinically important changes will be presented by clinical chemistry, coagulation and hematology parameter.

Proportions of subjects with elevated liver test (elevated alanine aminotransferase (ALT) or aspartate aminotransferase (AST) (≥ 3 ULN), and elevated Total bilirubin ($\geq 2x$ ULN)) will be summarized and individual subject data for subjects with potential Hy's law will be provided.

Key subject information will be also provided for subjects with treatment-emergent clinical chemistry, coagulation or hematology values outside predefined criteria.

Plots for ALT and AST versus total bilirubin, expressed as multiples of upper limit of normal (ULN) and liver biochemistry test results over time will be created. The reference lines are 3x ULN for ALT, AST, and 2x ULN for Total bilirubin. In each plot, total bilirubin will be in the vertical axis.

Laboratory reference ranges as well as all individual laboratory data will be listed. Liver assessments, liver risk factors and liver signs and symptoms for all potential Hy's law cases will be listed separately.

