6 CHANGES OF ANALYSES FROM PROTOCOL

1. Laboratory: The frequency of changes with respect to normal ranges between baseline and each post-treatment time point won't be tabulated. Instead the frequency will be presented for changes between baseline and maximum on treatment only.
2. The number and percentages of subjects with at least one dose interruption and at least one dose reduction will not be presented separately for the planned length of cycles but overall only.
3. Clarification: Given the decision on 14 December 2021 to terminate enrolment, the abbreviated CSR will focus on reporting of safety endpoints as there were a limited number of patients with evaluable data to give meaningful efficacy and CCI [REDACTED]. This was noted in the CSP v9.0 but has been further clarified with additional details of planned analyses in this SAP.

Early Phase Oncology Statistical Analysis Plan

Study Code D6132C00001

Edition Number 2.0

Date 05MAY22

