TFL number	Title	Template	Abbreviated CSR
Table 14.3.2.11	Number of subjects with adverse events leading to dose reduction of study interventions by system organ class and preferred term (Safety)	S22	X
Table 14.3.2.12	Number of subjects with adverse events leading to dose interruption of study interventions by system organ class and preferred term (Safety)	S22	X
Table 14.3.2.13	Number of subjects with adverse events leading to dose modification of study interventions by system organ class and preferred term (Safety)	S22	X
Table 14.3.3.1.1	All Deaths (Safety)	TDT010	X
Table 14.3.3.1.2	Number of subjects with adverse events with outcome of death, by system organ class and preferred term (Safety)	S13(i)	X
Table 14.3.3.2	Listing of deaths (Enrolled)	TDT040	X
Table 14.3.3.3	Adverse events with outcomes of death – key subject information (Safety)	S14	X
Table 14.3.4.1.1	Number of subjects with serious adverse events, by system organ class and preferred term (Safety)	S17(i)	X
Table 14.3.4.1.2	Number of serious adverse events, by system organ class and preferred term (Safety)	S16(ii)	X
Table 14.3.4.1.3	Number of subjects with serious adverse events, judged by investigator as possibly related to study interventions (Safety)	S17(ii)	X

TFL number	Title	Template	Abbreviated CSR
Table 14.3.4.2	Serious adverse events - Listing of key information for SAEs (Safety)	TAE180	X
Table 14.3.5.1	Number of subjects with adverse events leading to discontinuation of study intervention, by system organ class and preferred term (Safety)	S19(i)	X
Table 14.3.5.2	Adverse events leading to discontinuation of study interventions – key subject information (Safety)	TAE210	X
Table 14.3.6.1	Adverse events of special or potential interest of durvalumab - list of preferred terms	AS9	X
Table 14.3.6.2	Number of subjects with adverse events of special or potential interest of durvalumab by system organ class and preferred term (Safety)		X
Table 14.3.6.9	Adverse events of special or potential interest of durvalumab - Listing of key information (Safety)	TAE250	X
Table FDAAA1	Non-serious adverse events occurring in greater than 5% of subjects (Safety)	FDAAA1	(FDA)
Table 14.3.7.1.1	Clinical chemistry, coagulation and hematology laboratory variables over time (Safety)	S25(lab)	X
Table 14.3.7.1.2	Clinical chemistry, coagulation and hematology laboratory variables, CTCAE grade change from baseline to maximum on treatment (Safety)	TLAB020	X

TFL number	Title	Template	Abbreviated CSR

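### SAP 3.2.3.5 and 4.2.3.3 disagree on which laboratory parameters get change from baseline, and the grade-shift subset omits lymphocytes, the one AZD2811 blood-count risk it does not cover

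*SAP*

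**What the plan says.** **Change from baseline.** SAP 3.2.3.5 states: "Change from baseline in hematology and clinical chemistry will be calculated for a subset of parameters at each post-dose visit". The list that follows has four hematology, eight chemistry and two coagulation parameters. SAP 4.2.3.3 states: "Clinical chemistry, coagulation and hematology results and change from baseline will be summarized using descriptive statistics". It sets no limit on parameters beyond their being continuous.

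**Grade shift.** SAP 4.2.3.3 brings in the subset only here: "For a subset of laboratory variables (see Section 3.2.3.5) included in the current version of CTCAE, the CTCAE grade change from baseline" to the maximum on treatment is summarised by phase. The output is Table 14.3.7.1.2, whose title in Appendix A mentions no subset.

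**Protocol.** For hematology and clinical chemistry, protocol 9.4.4 says: "The frequency of changes with respect to normal ranges between baseline and each post-treatment time point will be tabulated". No parameters are excluded. The same section says that changes to the safety analysis will be described in full in the SAP and confined to cases where a listing suits better than a summary.

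**Declared changes.** SAP Section 6 drops the shift at each time point and continues: "Instead the frequency will be presented for changes between baseline and maximum on treatment only".

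**Risk table.** Protocol Table 6 includes "lymphocytopenia and leukocytopenia" among the potential risks of AZD2811.

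**The concern.** A programmer reading 3.2.3.5 would put change-from-baseline columns in Table 14.3.7.1.1 for 14 parameters. One reading 4.2.3.3 would do so for every continuous result. The choice should not be left to programming.

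The content of the subset matters as well, because the abbreviated CSR is centred on safety. Protocol 8.3.5 says laboratory results will be summarised in the CSR. For that reason it restricts AE reporting of laboratory deterioration to cases that are serious, cause discontinuation or are judged clinically relevant. The laboratory tables are therefore meant to carry the changes without symptoms. If a count tied to a named risk of the experimental drug has no row in the shift table, the reader cannot see there how many participants moved from a given baseline grade to a worse one.

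A reader comparing the protocol with SAP Section 6 would also not learn that the shift analysis now covers fewer parameters and uses different categories.

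**Working it through.** The point depends on no sample size, error rate or event figure. The check is a comparison of text and some counting.

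**1. Size of the subset (SAP 3.2.3.5).**
- Hematology: haemoglobin, WBC, ANC, platelets = 4
- Chemistry: albumin, creatinine, creatinine clearance, total bilirubin, AST, ALT, amylase, lipase = 8
- Coagulation: INR, fibrinogen = 2
- Total: 4 + 8 + 2 = 14

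**2. Rules within the SAP.**

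| Analysis | 3.2.3.5 | 4.2.3.3 |
|---|---|---|
| Change from baseline | 14-parameter subset | all continuous chemistry, coagulation and hematology |
| CTCAE grade shift | not mentioned | the 3.2.3.5 subset, where the variable is in CTCAE |

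There are two rules for change from baseline and one for the grade shift. The conflict is in the first row.

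**3. Coverage of the AZD2811 blood-count risks in protocol Table 6.** Febrile neutropenia and sepsis are not counted, because a blood count alone does not establish them.

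| Risk | Status in Table 6 | Count | In subset? |
|---|---|---|---|
| Neutropenia | identified | ANC | yes |
| Leukocytopenia | potential | WBC | yes |
| Anemia | potential | haemoglobin | yes |
| Thrombocytopenia | potential | platelets | yes |
| Lymphocytopenia | potential | lymphocytes | **no** |

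Coverage is 4 of 5. Lymphocytes are collected in the white-cell differential (protocol Table 18). SAP 3.2.3.5 derives the absolute count when it is not reported and has CTC grade calculated at each visit. Adding them gives 5 of 5 and 14 + 1 = 15 parameters.

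**4. Protocol 9.4.4 against the SAP shift analysis.**

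| Feature | Protocol 9.4.4 | SAP 4.2.3.3 | Declared in SAP Section 6? |
|---|---|---|---|
| Time points | each post-treatment time point | maximum on treatment | yes |
| Parameters | hematology and chemistry, no subset | subset | no |
| Categories | normal range | CTCAE grade | no |

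Of three differences, one is declared. Appendix A lists no normal-range shift table.

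**5. Where lymphocytes can still appear.** None of these outputs is stated to be limited to the subset:
- Table 14.3.7.1.1, values over time
- Table 14.3.7.1.3, clinically important changes, which SAP 3.2.3.5 defines as CTCAE Grade 2 or higher, or a change to Grade 3 or 4
- Table 14.3.7.2, individual information on participants with out-of-range values
- Appendix 16.2.8.2, all results, with high and low values flagged

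The definition behind Table 14.3.7.1.3 comes after the subset list in the same section, so its scope is open to misreading.

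**The case against.** The strongest reply is that nothing goes unreported. Table 14.3.7.1.3 gives numbers and percentages by hematology parameter, and on its face that includes Grade 3-4 lymphocyte values. With only 9 participants treated with AZD2811 plus durvalumab, the key-subject table and flagged listings are highly informative. The sentence in 3.2.3.5 is probably misworded: 4.2.3.3 ties the subset to the shift table, and the SAP amendment history describes it the same way. The subset is also printed by name in the SAP, so its absence from Section 6 is a gap in documentation.

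Much of this stands. A reader might infer that a Grade 3-4 lymphocyte fall could be missed altogether, and that with 1/9 = 11.1 percentage points per participant the reported rate would be badly wrong. The documents do not support that, because the outputs above remain open to lymphocytes. The 11.1 points describe any single event among nine and measure no loss. A reader might also count three conflicting definitions, but the protocol's normal-range shift is a different analysis. Nor does the argument require rows for alkaline phosphatase, electrolytes, magnesium or glucose. Magnesium, for one, is required only at screening and Cycle 1 Day 1, then as clinically indicated or per local practice (protocol Table 17), so a shift would rest on selectively collected values.

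The reply does not remove the contradiction. It also does not replace the shift row. A Grade 2 or higher count includes a participant who was already Grade 2 at baseline and did not worsen, and it misses a move from Grade 0 to Grade 1. The key-subject table does not summarise worsening by grade.

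**Conclusion.** The point holds in this limited form. SAP 3.2.3.5 and 4.2.3.3 give incompatible rules for change from baseline. The shift subset covers four of five AZD2811 blood-count risks and leaves out lymphocytes, with no reason given. Two of the three differences from the protocol's laboratory shift are not declared in Section 6. The loss is confined to the cross-tabulation of baseline grade against worst grade for one parameter.

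Two limits apply. Lymphocytopenia is a potential risk of AZD2811, not an identified one. And a shift row would show on-treatment worsening, not relatedness to AZD2811: SAP 3.1.2 uses the pre-induction baseline for both phases, so a shift in maintenance can also reflect the induction chemotherapy. The verdict assumes that Table 14.3.7.1.3 will be produced for all gradable parameters, as 4.2.3.3 suggests. If it were limited to the subset, lymphocyte grades would have no summary table by grade and the point would weigh more.

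**What to change.** 1. In SAP 3.2.3.5, state that change from baseline is calculated for all continuous chemistry, coagulation and hematology parameters, as in 4.2.3.3, and that the subset applies only to Table 14.3.7.1.2.
2. Add absolute lymphocyte count to the subset, and note the subset in a footnote to that table.
3. State that Table 14.3.7.1.3 is not limited to the subset.
4. In SAP Section 6, declare the parameter subset and the switch from normal-range to CTCAE categories as departures from protocol 9.4.4.

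The cost is one more row in one table, from counts and grades the SAP already derives, plus a few sentences of text. No new data are needed.

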5.1 Induction Phase Inclusion Criteria

Participants are eligible to be included in the study only if all of the following criteria apply:

Age

- 1 Participant must be \geq 18 years of age, at the time of signing the informed consent.

Type of Participant and Disease Characteristics

- 2 Histologically or cytologically documented extensive stage (American Joint Committee on Cancer Stage [7th edition] IV SCLC [T any, N any, M1 a/b]), or T3 or T4 tumor stage due to multiple lung nodules that are too extensive or have tumor/nodal volume that is too large to be encompassed in a tolerable radiation plan.
 - Brain metastases; must be asymptomatic or treated and stable off steroids and anti-convulsants for at least one month prior to study treatment. Participants with suspected brain metastases at screening should have a computed tomography (CT)/magnetic resonance imaging (MRI) of the brain prior to study entry.
- 3 Provision of an archived tumor tissue block or unstained slides if block cannot be provisioned) where such samples exist. If not, a mandatory fresh biopsy will be required at screening (refer to Section 8.6.2.1 and Laboratory Manual for details).
- 4 Participants must be considered suitable to receive a platinum-based chemotherapy regimen, combined with durvalumab, as first-line treatment for the ES-SCLC. Chemotherapy must contain either cisplatin or carboplatin in combination with etoposide.
- 5 Life expectancy \geq 12 weeks.
- 6 World Health Organization (WHO) Eastern Cooperative Oncology Group (ECOG) Performance Status of 0 or 1 at treatment assignment.
- 7 Body weight $>$ 30 kg.
- 8 At least one lesion, not previously irradiated, that can be accurately measured at baseline as \geq 10 mm in the longest diameter (except lymph nodes, which must have a short axis \geq 15 mm) with CT or MRI and that is suitable for accurate repeated measurements as per RECIST v1.1 guidelines.
- 9 No prior exposure to immune-mediated therapy including, but not limited to anti-PD-1, anti-PD-L1, and anti-PD-L2 antibodies, excluding therapeutic anticancer vaccines.
- 10 Adequate organ and marrow function as defined below:

- Hemoglobin ≥ 9.0 g/dL (without blood transfusion in the last 2 weeks).
- Absolute neutrophil count $\geq 1.5 \times 10^9/L$ (use of granulocyte colony stimulating factor is not permitted at screening).
- Platelet count $\geq 100 \times 10^9/L$ (without platelet transfusion in the last 2 weeks).

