5.3.1 Maintenance Phase Inclusion Criteria

- 1 Body weight > 30 kg.
- 2 Adequate organ and marrow function as defined below:
 - Absolute neutrophil count $\geq 1.5 \times 10^9/L$.
 - Platelet count $\geq 75 \times 10^9/L$.
 - Serum bilirubin $\leq 1.5 \times$ ULN.
 - In participants without hepatic metastasis: ALT and AST $\leq 2.5 \times$ ULN.
 - In participants with hepatic metastases: ALT and AST $\leq 5 \times$ ULN.
 - Measured or calculated creatinine CL: > 50 mL/min, as determined by Cockcroft-Gault (using actual body weight) (see Section 5.1).

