3.1.2 Baseline measurements and change from baseline variables

Baseline will be the last non missing value obtained prior to the first administration of study intervention in induction phase and any information taken after first administration of study intervention will be regarded as post baseline information. All changes from baseline analyses use this definition of baseline regardless of the period being analyzed, e.g. no baseline for maintenance phase will be defined.

If two visits are equally eligible to assess subject status at baseline (e.g., screening or re-screening and baseline assessments both on the same date prior to first administration with no washout or other intervention in the screening period), the average should be taken as the baseline value. For non-numeric laboratory tests (i.e. some of the urinalysis parameters) where taking an average is not possible then the best value would be taken as baseline as this is the most conservative. In the scenario where there are two assessments on Day 1, one with time recorded and the other without time recorded, the one with time recorded would be selected as baseline. Where safety data are summarized over time, study day will be calculated in relation to date of first study intervention in induction phase. If no value exists before the first study intervention, then the baseline value will be treated as missing.

In all summaries change from baseline variables will be calculated as the post treatment value minus the value at baseline. For % change from baseline, calculate:

$$(\text{Post baseline value} - \text{Baseline value}) / \text{Baseline value} \times 100$$

Study day will be calculated as:

$$\text{Date of assessment} - \text{Date of first dose/administration of study intervention in induction phase} + 1$$

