3.2.3.4 Adverse Events

An adverse event (AE) is the development of any untoward medical occurrence in a subject or clinical study participant administered a medicinal product and which does not necessarily have a causal relationship with this treatment. The full definition of AEs and serious AEs (SAEs) can be found in the CSP Appendix B.

AEs and SAEs will be collected throughout the study, from date of informed consent until 90 days after the last dose of study intervention. Events will be defined as treatment emergent if they started after dosing or prior to dosing and worsen following study intervention. AEs which start in induction phase and subsequently worsen in maintenance phase will be defined as treatment emergent for both phases. AEs which start in induction phase and are ongoing, but not worsened, in maintenance phase, will be presented for induction phase only. For dosing days, AE start timing will be collected as well to identify pre- or post-dose AEs. AEs which start on Cycle 1 Day 1 but with start time before dosing are not considered treatment emergent. AEs which start/worsen on CCI [REDACTED] but with start time before dosing are considered as treatment emergent for induction phase only as long as they do not worsen in maintenance phase afterwards.

AEs with start or worsening date in safety follow-up period (within 90 days after the last dose of study intervention) will be presented along with AEs occurring in the phase from which the subject discontinued.

A flag will be created to indicate AEs which occur within the 90 days safety follow-up period but after initiation of the first subsequent therapy following discontinuation of study intervention.

The Medical Dictionary for Regulatory Activities (MedDRA) (using the latest or current MedDRA version) will be used to code the AEs. AEs will be graded according to the National Cancer Institute Common Terminology Criteria for AEs (CTCAE Version 5.0).

Maximum CTCAE grades on treatment overall and by phase will be derived.

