Table 14.3.7.1.3	Clinically important changes in clinical chemistry, coagulation and hematology laboratory variables parameters (Safety)	TLAB060	X
Table 14.3.7.1.4	Proportion of subjects with elevated liver test based on measured laboratory values (Safety)	AS15	X
Table 14.3.7.1.5	Subjects with potential Hy's Law – individual subject data (Safety)	S32	X
Table 14.3.7.2	Clinical chemistry, coagulation and hematology laboratory variables, treatment-emergent changes outside local reference range – key subject information (Safety)	S28	X
Table 14.3.8.1	Vital signs variables, over time (Safety)	S25(vital)	X
Table 14.3.8.2	Vital signs variables, treatment-emergent changes outside predefined criteria – key subject information (Safety)	S28	X
Table 14.3.8.3	ECG variables over time (Safety)	S25(ecg)	X
Table 14.3.8.4	ECG, baseline versus last observation on treatment (Safety)	S41(ecg)	X
Table 14.3.8.5	QTcF, QTcf intervals and QTcB, at any observation on treatment (Safety)	S35	X
Figure 14.2.2.1	Individual total AZD2811 blood concentration-time plots - Log scale (Pharmacokinetics)	PK1	X
Figure 14.2.2.2	Individual metabolite (AZ12102238) blood concentration-time plots – Log scale (Pharmacokinetics)	PK1	X

TFL number	Title	Template	Abbreviated CSR
Figure 14.2.2.3	Geomean +/- gSD total AZD2811 blood concentration-time plots – Log scale (Pharmacokinetics)	PK1	X
Figure 14.2.2.4	Geomean +/- gSD metabolite (AZ12102238) blood concentration-time plots – Log scale (Pharmacokinetics)	PK1	X
Figure 14.3.7.1	ALT versus total bilirubin, expressed as multiples of ULN (Safety)	S9	X
Figure 14.3.7.2	AST versus total bilirubin, expressed as multiples of ULN (Safety)	S9	X
Figure 14.3.7.3	Liver biochemistry test results over time – subjects with elevated ALT or AST, and elevated total bilirubin, at any time (Safety)	S10	X
Appendix 16.2.1	Discontinued subjects	APL01	X
Appendix 16.2.1	Subjects with important protocol deviations	APL03	X
Appendix 16.2.2	Subjects affected by the global/country situation	APL24	X
Appendix 16.2.3	Subjects affected by the global/country situation - details	APL25	X
Appendix 16.2.3.1	Subjects excluded from analysis set	APL04	X
Appendix 16.2.4.1	Demographic and baseline characteristics, Assigned to study intervention	APL06	X
Appendix 16.2.4.2.1	Radiotherapy prior to treatment and post treatment, Assigned to study intervention		X

TFL number	Title	Template	Abbreviated CSR

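### SAP 3.2.3.5 defines a clinically important laboratory change without reference to baseline, so Table 14.3.7.1.3 as specified would count grades that stayed the same or improved

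*SAP*

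**What the plan says.** SAP 3.2.3.5 (Laboratory Data) has CTCAE grades calculated at each visit, takes the maximum post-baseline grade by study phase and overall, and then gives the definition: "Clinically important changes are defined as CTCAE grade ≥ 2 or changes to CTCAE grade 3 or 4". These changes are derived by phase and overall.

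SAP 4.2.3.3 (Laboratory) uses the term without adding to it: "Number and percentages of clinically important changes will be presented by clinical chemistry, coagulation and hematology parameter". The output is Table 14.3.7.1.3 in SAP Appendix A, built on template TLAB060. Its title repeats the term and adds no requirement that the value worsen. No other section of the protocol or SAP defines a clinically important laboratory change.

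A different output does compare with baseline. For a subset of laboratory variables, SAP 4.2.3.3 says that "the CTCAE grade change from baseline to maximum on treatment will be summarized by phase"; this is Table 14.3.7.1.2.

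**The concern.** The term being defined is a change, but the first clause describes a state: any Grade 2 or higher. A subject who enters at Grade 2 and stays there satisfies it. So does one who enters at Grade 3 and improves to Grade 2. The second clause, on changes to Grade 3 or 4, selects nobody whom the first has not already selected. A definition with a clause that does no work has usually lost a word, here probably the word that made the first clause a rise of two or more grades.

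The abbreviated CSR is meant to report safety in full, and this table would carry a title that its content does not meet. The error runs in one direction: it adds subjects who did not worsen and misses none who did under the likely intended rule.

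**Working it through.** The SAP gives no figure on this point, so there is nothing of its own to reproduce. The check enumerates the grade pairs.

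**Inputs**
- *b*, baseline grade, 0 to 4. Baseline is the last value before the first induction dose (SAP 3.1.2).
- *m*, maximum post-baseline grade, 0 to 4 (SAP 3.2.3.5). Using the maximum loses nothing: each rule below, if met at one grade, is met at any higher grade.
- 9 subjects received AZD2811 + durvalumab (Protocol 9.4).

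**Rules**
- A, as written: *m* ≥ 2, or *m* is 3 or 4 and differs from *b*.
- B, likely intent: *m* − *b* ≥ 2, or *m* > *b* with *m* ≥ 3.
- C, any worsening to Grade 2 or above: *m* > *b* and *m* ≥ 2.

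**Step 1: does the second clause do anything?** Grade 3 or 4 is already Grade ≥ 2, so under rule A it adds 0 pairs. If the first clause meant a rise of at least 2 grades, the second would add 2→3 and 3→4. Both clauses then have a purpose.

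**Step 2: what rule A counts.** For each of 5 baseline grades it counts *m* = 2, 3 and 4, so 5 × 3 = 15 of 25 pairs. Those with *m* ≤ *b* are 2→2, 3→3 and 4→4 (unchanged) and 3→2, 4→2 and 4→3 (improved), 6 in all.

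**Step 3: the alternatives, by baseline grade 0 to 4.**
- B: 3 + 2 + 2 + 1 + 0 = 8 pairs, none without worsening.
- C: 3 + 3 + 2 + 1 + 0 = 9 pairs, none without worsening (15 − 6 = 9).
- B and C differ only in 1→2.

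**Step 4: dependence on baseline severity.** The documents give neither CTCAE cut-points nor baseline grades, so the highest baseline grade is an assumption:

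| Baseline grades allowed | Pairs | A counts | of which not worsened | B counts | C counts |
|---|---|---|---|---|---|
| 0–4 | 25 | 15 | 6 | 8 | 9 |
| 0–3 | 20 | 12 | 3 | 8 | 9 |
| 0–2 | 15 | 9 | 1 (2→2) | 7 | 8 |
| 0–1 | 10 | 6 | 0 | 5 | 6 |

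Protocol 5.1 sets entry limits for hemoglobin, neutrophils, platelets, bilirubin, ALT, AST and creatinine clearance. That makes the lower rows likelier for those parameters and leaves 2→2 as the most plausible pair without worsening. Some abnormality is still allowed at entry, for example hemoglobin down to 9.0 g/dL, or ALT and AST up to 5 × ULN with hepatic metastases.

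**Step 5: scale.** With a denominator of 9, one subject counted without worsening moves a percentage by 1/9 = 11.1 points. This shows sensitivity only. Pairs are not frequencies, and the documents do not say how many subjects fall in any pair.

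**The case against.** The strongest reply is that the sentence is about changes, so its first clause can be heard as a change of two or more grades, which gives both clauses work. Template TLAB060, which the documents do not show, may state that condition. The first part is probably what was meant, but the text does not say it, and a SAP should not rely on an unseen template to correct its own definition.

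The second reply concerns consequence, and most of it stands. The analysis is descriptive (SAP 4). Table 14.3.7.1.2 would show 2→2 or 3→2 as no worsening for its parameters. Laboratory deteriorations that the investigator considers clinically relevant are reported as AEs (Protocol 8.3.5), and all individual laboratory data are listed (SAP 4.2.3.3). The cover is not complete: the shift table is limited to a subset of variables, while the sentence on clinically important changes states no such limit. For other parameters a reader may have only the listings.

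Three stronger readings are tempting, and the documents do not support them.

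- **That 1→2 is also an over-count.** It drops out under rule B, but it is a real worsening, and no section settles whether it is clinically important. The excess that is wrong on any reading is 6 pairs, not 7.
- **That the single baseline is an error for the maintenance columns.** SAP 3.1.2 applies the pre-induction baseline "regardless of the period being analyzed, e.g. no baseline for maintenance phase will be defined", and Protocol 9.4.1 and 9.4.4 specify the same baseline. A reader might set this against the AE rule ("AEs which start in induction phase and are ongoing, but not worsened, in maintenance phase, will be presented for induction phase only"), but that rule deals with onset and worsening of events, whereas the laboratory tables report a phase maximum. A summary referenced to the start of maintenance would be a preference, not a correction.
- **That the parameter list in SAP 3.2.3.5 measures exposure to the problem.** That list governs change from baseline and the shift table. It is not shown to govern Table 14.3.7.1.3.

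**Conclusion.** The point holds, and it is minor. As written, the definition has no baseline comparison, its second clause is redundant, and 6 of the 15 grade pairs that it counts are unchanged or improved. If baselines above Grade 2 do not occur, only 2→2 remains; if baselines above Grade 1 do not occur, none does. The conclusion assumes that the SAP text is programmed as it stands and that TLAB060 adds no worsening condition.

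A reader might infer that the safety report would be materially misleading. The documents do not support that: the number of affected subjects is unknown and could be zero, and the shift table and listings allow most cases to be checked.

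**What to change.** In SAP 3.2.3.5, replace the definition with: *an increase of at least 2 CTCAE grades from baseline, or any worsening from baseline to CTCAE Grade 3 or 4*. Repeat it as a footnote to Table 14.3.7.1.3, and check that TLAB060 is programmed to match. If the sponsor wants 1→2 to count, *any worsening from baseline to Grade 2 or above* also removes all six pairs; the SAP should state which rule applies.

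The cost is one reworded sentence and one footnote. No new data, extra table or second baseline is needed. SAP edition 2.0 is dated 5 May 2022 and the data cut-off is planned for 18 June 2022; a change made before that cut-off would not be post hoc.
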